# 2.2 MODIFIED INTENT-TO-TREAT (MITT) POPULATION

The mITT population will include all patients in the Safety/ITT population, who have at least one postbaseline disease assessment (at least one post-baseline imaging assessment in accordance with RECIST 1.1, or documented clinical progression [every effort should be made to objectively assess radiographic progression]), or reported death during the treatment period

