	Substudy 2 A Simon's two-stage design will be used in Substudy 2. The null hypothesis (H 0 ) that the true 3-month rate of progression-free survival (PFS3) is $p_0 \le 0.45$ will be tested against a one-sided alternative. In the first stage, 15 mITT-evaluable patients will be accrued. If there are 7 or fewer patients with PFS 3 in these 15 patients, then Substudy 2 will be stopped. Otherwise, 28 additional mITT-evaluable patients will be accrued for a total of 43. H 0 will be rejected if a PFS 3 is observed in 25 or more of these 43 patients. The type I error rate is 0.0481, and power is approximately 0.8 when the true PFS3 rate for derazantinib is $p_1 = 0.65$ .
	All patients who receive at least one dose of derazantinib capsules will be considered evaluable for safety analyses.
Data Monitoring Committee:	The Data Monitoring Committee (DMC) will be established to ensure the safety of study patients and the validity of study results. The DMC composition and operation will be described in the DMC Charter. The DMC may recommend study termination or continuation based on periodic review of safety and/or efficacy data in this study.

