# **10.6** Efficacy analyses

All efficacy endpoints will be summarized on the data from patients. All analyses will include summary statistics, including number of patients (n) and percentage (%) for categorical variables and number of patients, mean, standard deviation, median, minimum, and maximum for continuous variables. Two-sided exact 95% confidence intervals (CIs) based on the large sample assumption will be provided where appropriate. Time-to-event analyses will be performed using Kaplan-Meier (KM) methods.

# 10.6.1 Primary efficacy parameter Substudy 1

The primary efficacy endpoint will be ORR, defined as the achievement of confirmed CR or PR using RECIST v1.1, as assessed by the central radiology reviewers. Point estimates and 2-sided 95% CIs will be provided. Hypothesis testing will be performed for H0: ORR=0.1 versus Ha: ORR=0.23 at the interim and final analyses as specified:

The decision rules are specified as:

• If the interim one-sided p-value, p1 > 0.5 (i.e., the observed ORR is less than 10%), the trial will stop due to futility; otherwise, the trial will continue to the second stage. At the final stage, if the p-value is ≤ to 2.5% (one-sided), or equivalently the lower limit of the CI is ≥ 10%, the null hypothesis will be rejected.

In the final analysis, the ITT population will be the primary analysis population.

## Substudy 2

The primary efficacy endpoint will be progression-free survival at 3 months (PFS 3) based on survival status or central radiology review RECIST 1.1. For Substudy 2, a Simon's twostage design will be used, with approximately 15 patients in Stage 1, and an additional 28 patients if the study proceeds to Stage 2. H0 will be rejected if a PFS 3 is observed in 25 or more of these 43 patients. The type I error rate is 0.0481, and power is approximately 0.8 when the true PFS 3 rate for derazantinib is p1 = 0.65.

The mITT population will be the primary analysis population.

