#### **Substudy 1**

To prove the drug effect over placebo in ORR in this single-arm pivotal study, the hypothesis was specified as

$$H_0: ORR \le 0.10 \text{ and } H_a: ORR \ge 0.10.$$

The hypothesis test will be performed at a one-sided 2.5% significance level. A 10% response rate is chosen for the null hypothesis (H0), which is much higher than the observed placebo rate  $7\sim8\%$  in larger historical trials and publications (Lamarca 2014). The 23% response rate under the alternative hypothesis is estimated for power and sample size calculations.

Approximately 100 patients will be enrolled for this two-stage group sequential study with futility stopping.

An interim analysis for futility was planned to be performed when 40 patients who satisfy mITT criteria had at least one post baseline tumor evaluation. The study was to be terminated for futility if 4 or fewer responses were observed among 40 evaluable patients. If the treatment was ineffective, i.e., ORR=0.1, the probability of futility stopping was 63%. If the true response rate ORR=0.23, the probability of futility stopping was only 3%. The design provided approximately 90% power to reject the null hypothesis at one-sided significance level 0.025, or equivalently to have the lower bound of confidence interval of ORR > 10%. If 5 or more objective responses (OR) were observed and confirmed based on central radiology review prior to enrollment of 40 evaluable patients, the interim analysis was to be performed based on fewer than 40 patients.

The interim analysis was performed on 29 patients satisfying the mITT criteria. At the time of analysis 6 patients (21%) had a confirmed central PR, and futility was rejected per DMC recommendation.

#### Substudy 2

A Simon's two-stage design will be used in Substudy 2. The null hypothesis (H0) that the true 3-month rate of PFS 3 is  $p_0 \le 0.45$  will be tested against a one-sided alternative. In the first stage, approximately 15 mITT-evaluable patients will be accrued. If there are 7 or fewer patients with PFS 3 in these 15 patients, then Substudy 2 will be stopped. Otherwise, 28 additional mITT-evaluable patients will be accrued for a total of up to approximately 43. H0 will be rejected if a PFS 3 is observed in 25 or more of these 43 patients.

The type I error rate is 0.0481, and power is approximately 0.8 when the true PFS 3 rate for derazantinib is  $p_1 = 0.65$ .

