\* If a CR is truly met at first time point, then any disease seen at a subsequent time point, even disease meeting PR criteria relative to baseline, makes the disease PD at that point (since disease must have reappeared after CR). Best response would depend on whether minimum duration for SD was met. However, sometimes 'CR' may be claimed when subsequent scans suggest small lesions were likely still present and in fact the patient had PR, not CR at the first time point. Under these circumstances, the original CR should be changed to PR and the best response is PR.

For patients with non-measurable disease, SD should be replaced by non-CR/Non-PD

If the best overall response has any special cases or difficulty from unexpected data, then these may be checked and discussed with the study team to decide which best overall response is best suited.

As specified in RECIST 1.1, repeated 'NE' time point assessments complicate best response determination. Should a CR/PR be followed by one or more NE response and then a CR/PR, then confirmed response would be achieved (as an example PR-NE-PR will be considered as a confirmed response).

Patients without efficacy assessments are considered non-responders, and included in the analysis.

Hypothesis testing (null hypothesis  $[H_0]$  versus alternative hypothesis  $[H_A]$ ) were performed at the interim and will be performed in the final analyses as specified below:

Null Hypothesis H0: ORR  $\leq 0.10$  and Alternative Hypothesis HA: ORR > 0.10

The hypothesis testing will be performed using exact test for binomial proportion at a one-sided 2.5% significance level. Point estimates and exact 2-sided 95% confidence intervals (Clopper-Pearson) will be provided. If the p-value is  $\leq$  to 2.5% (one-sided), or equivalently the lower limit of the confidence interval is > 10%, the null hypothesis will be rejected.

Considering the number of patients per site planned in this study, the site effect and treatment by site interaction will not be evaluated.

#### Substudy 2

The primary efficacy endpoint for Substudy 2 will be the proportion of patients who have PFS at 3 months from the first date of receiving study drug as assessed by survival status or central radiology review RECIST 1.1.

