A Simon's two-stage design will be used, with approximately 15 patients in Stage 1, and an additional 28 patients if the study proceeds to Stage 2.  $H_0$  will be rejected if a PFS 3 is observed in 25 or more of these 43 patients. The type I error rate is 0.0481, and power is approximately 0.8 when the true PFS 3 rate for derazantinib is p1 = 0.65.

Point estimates, exact 2-sided 95% confidence intervals (Clopper-Pearson) and associated p-value will be provided.

PFS will be analyzed using Kaplan-Meier methodology (Kaplan & Meier 1958). The median duration of PFS will be presented along with the standard error and 2-sided 95% CI. If they are calculable, the 25th and 75th percentiles and the 2-sided 95% CIs around the percentiles will be presented. Kaplan-Meier estimates at 3, 6, 9 and 12 months will also be presented. The Kaplan-Meier survival curves will also be presented.

Additional PFS sensitivity analyses which consider alternative censoring methods as outlined in FDA guidelines (FDA 2018, FDA 2015) will be conducted in the same manner, as described above. These will be performed for the Safety/ITT and mITT populations:

- Sensitivity analysis 1 in Table 3 uses a conservative approach by assigning the date of discontinuation, or missed tumor assessment followed by PD or death as an event date.
- Sensitivity analysis 2 in Table 4 includes clinical progression as an event.
- Sensitivity analysis 3 in Table 5 evaluates PFS including post EOT radiological assessments.

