# 4 CHANGES FROM PLANNED ANALYSIS

- The protocol indicates the primary analysis population is restricted to FISH performed by a central laboratory. However, this was not the case and therefore reference to central FISH has been removed
- Safety/ITT Population has been updated from "All patients who receive any amount of study drug" to 2 separate definitions for each substudy to take into consideration the substudy that each patient was enrolled in:
  - The Safety/ITT population for Substudy 1 will include all patients with locally or centrally confirmed *FGFR2* fusions/rearrangements who receive any amount of study drug.
  - The Safety/ITT population for Substudy 2 will include all patients with locally confirmed *FGFR2* mutations or amplifications who receive any amount of study drug.
- The mITT population definition was updated from "All patients who receive any amount of study drug and have at least one post-baseline disease assessment." to "All patients in the Safety/ITT population, and have at least one post-baseline disease assessment (at least one post-baseline imaging assessment in accordance with RECIST 1.1, or documented clinical progression [every effort should be made to objectively assess radiographic progression]). Patients who have primary reason for discontinuation as death will be included in the mITT population."
- The PP population was updated from "All patients in the mITT Population who have no major protocol violations during the study, receive at least one cycle (28 doses) of ARQ 087, have at least one post-baseline efficacy measurement, and test positive for FGFR2 gene fusion by the central laboratory" to "will include all patients in the mITT population who have no important protocol (IPD) deviations which are determined to potentially impact efficacy analyses during the study. Protocol deviations will be identified prior to final analysis." This was to reflect the Labcorp standard to use "important" rather than "major", and furthermore to allow flexibility in defining those IPDs that may affect the efficacy endpoints.
- DCR has been added as an exploratory efficacy endpoint, and is defined as the achievement of confirmed CR or PR or SD (or Non-CR/Non-PD for patients with non-measurable disease).

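### SAP 2.2 and SAP 4 give non-equivalent death clauses for the Substudy 2 primary population (mITT), and both can leave out an early death that is a PFS3 failure

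*SAP*

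**What the plan says.** Protocol 10.6.1 fixes the analysis set for Substudy 2: "The mITT population will be the primary analysis population". SAP 3.2.7 agrees and keeps ITT and per-protocol as sensitivity sets.

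The mITT definition appears in three places:

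- **Protocol 10.1** requires study drug and at least one post-baseline disease assessment. It has no death clause.
- **SAP 2.2** takes Safety/ITT patients with a post-baseline scan or documented clinical progression, and adds: "or reported death during the treatment period".
- **SAP 4** sets out the updated definition with the same scan and clinical-progression routes, but a different last sentence: "Patients who have primary reason for discontinuation as death will be included in the mITT population".

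SAP 3.2.7.1 defines the Substudy 2 endpoint as the proportion of patients progression-free at 3 months, "as assessed by survival status or central radiology review RECIST 1.1". Success means PFS longer than 91 days. The same section says that deaths after the EOT visit are not PFS events, and it censors patients with no post-baseline tumor evaluation at first dose.

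The design in SAP 1.4 counts evaluable patients. Stage 1: "If there are 7 or fewer patients with PFS 3 in these 15 patients, then Substudy 2 will be stopped". Stage 2: "28 additional mITT-evaluable patients will be accrued for a total of up to approximately 43". The null is rejected at 25 or more successes in 43.

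**The concern.** SAP 4 reports the definition being adopted, so it should match SAP 2.2. It does not, and two programmers could build different denominators for the same primary test.

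The second problem remains whichever clause is used. Both routes into mITT for a patient who dies early are tied to treatment: death while in the treatment period, or death as the reason treatment ended. Neither is tied to the 91-day window that decides the endpoint. A patient can therefore have a known outcome under the endpoint definition (dead by day 91, hence not progression-free at 3 months) and still be outside the set in which the endpoint is counted. Accrual targets are set in mITT-evaluable patients, so such a patient would also be replaced. A patient who is dead by day 91 cannot be a success, so the effect runs in one direction only, in favor of the drug.

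**Working it through.** **Step 1. Compare the two clauses.** The SAP does not define the treatment period. Protocol 5.5 separates it from the 30-day safety follow-up, and the nearest SAP term (treatment phase duration, SAP 3.2.1) runs from C1D1 to the EOT visit. I use that reading. All three patients below have no post-baseline scan and no documented clinical progression.

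| Patient | SAP 2.2 | SAP 4 |
|---|---|---|
| Dies on treatment; death is the discontinuation reason | in | in |
| Stops for an adverse event; dies before the EOT visit | in | out |
| Stops before week 8 for a reason other than death; dies after EOT, by day 91 | out | out |

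The second row shows that the clauses differ. The third row is the patient whom both lose. The first scheduled scan is at week 8 (Protocol 6.9) and survival follow-up starts at the last dose (Protocol 5.6), so such a patient can exist and the death can be recorded.

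**Step 2. Reproduce the plan's figures.** Inputs, from SAP 1.4 and 3.2.7.1: p0 = 0.45, p1 = 0.65, n1 = 15, continue with 8 or more, 28 further patients, reject at 25 or more of 43.

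P(reject | p) = Σ (x = 8 to 15) P[Bin(15, p) = x] × P[Bin(28, p) ≥ 25 − x]

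- p = 0.45: 0.0481, as stated.
- p = 0.65: 0.8035, matching the stated power of about 0.8.

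**Step 3. Let k early deaths be excluded and replaced.** If 43 mITT patients are accrued and k further treated patients are excluded failures, the all-treated number is 43 + k. With an all-treated PFS3 rate of 0.45, the rate among mITT patients is 0.45 × (43 + k)/43. Put this into the Step 2 formula:

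| k (assumed) | Share of treated, k/(43 + k) | mITT rate | P(reject) |
|---|---|---|---|
| 0 | 0% | 0.4500 | 0.0481 |
| 1 | 2.3% | 0.4605 | 0.0633 |
| 2 | 4.4% | 0.4709 | 0.0818 |
| 3 | 6.5% | 0.4814 | 0.1040 |

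**Step 4. Put the deaths back.** Keep Stage 1 as it is, enlarge the total to 43 + k and hold the rejection threshold at 25. At p = 0.45 the type I error is 0.0624 for k = 1 (n = 44) and 0.0786 for k = 2 (n = 45). In both cases 26 successes would be needed to stay below 0.05 (0.0362 and 0.0480).

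**Step 5. The Stage 1 decision.** SAP 1.4 reports 8 successes in 14 mITT patients. One excluded death put back gives 8 of 15, which still passes because 8 exceeds 7. With two or more, the answer depends on enrolment order.

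**Step 6. Does changing the population wording suffice?** No. Once in mITT, the third patient of Step 1 meets two rules in SAP 3.2.7.1: the death is after EOT, so it is not an event, and there is no post-baseline scan, so PFS is censored at first dose. Such a patient would not exceed 91 days, but the SAP does not say how patients censored before day 91 are counted for PFS3.

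**The case against.** Several points on the other side stand.

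- **The SAP moved in the conservative direction.** The protocol's mITT has no death clause and does not name clinical progression. SAP 2.2 adds both and so brings early failures into the denominator. The gap is an unfinished improvement.
- **The case is narrow.** Protocol 5.4.4 and 6.9 call for an EOT scan unless a recent scan already showed progression, and ask for a tumor evaluation as soon as possible after discontinuation. Documented clinical progression alone qualifies for mITT. These measures reduce the number of such patients, though a scan cannot be guaranteed in a patient who is deteriorating.
- **The death is not always known.** Under Protocol 5.7.2 survival follow-up ends if consent for it is withdrawn, so the point covers known deaths only.
- **The effect will be visible.** ITT is a prespecified sensitivity set for Substudy 2, and SAP 3.2.1 tabulates reasons for exclusion. The decision rule is nevertheless applied in mITT.
- **SAP 4 is a list of changes.** A difference between superseded text and current text would not matter. Here, however, the differing sentence is in the definition being adopted. The two clauses could be read as loose versions of one intention, but Step 1 shows that they do not select the same patients.

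A reader might infer that the stated 0.0481 is wrong. The documents do not support that: the design is specified in mITT-evaluable patients, and the figure reproduces for them. They do not say that the 0.45 null is an all-treated rate. Step 3 answers a different question, namely how often the rule would declare success if the all-treated rate were 0.45.

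**Conclusion.** The point holds. SAP 2.2 and SAP 4 select different patients for the Substudy 2 primary population, and both can omit a treated patient whose death by day 91 makes PFS3 a failure. Any such omission can only raise the observed PFS3 rate.

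The size rests on two assumptions: an all-treated PFS3 rate of 0.45, and 0 to 3 excluded deaths, for which the documents give no count. On these, the chance of rejecting is 0.048 to 0.104, and one excluded death is enough to take it above 0.05. With none, nothing changes.

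A reader might infer that known failures were in fact dropped, or that the Stage 1 decision is unsafe. The documents show neither: they do not say how many treated patients are outside mITT, and 8 of 14 survives one such death. Nor is this a case against mITT as such. The SAP chose to count early deaths in mITT, and its wording does not carry that choice through to day 91. It should be corrected.

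**What to change.** 1. Use one mITT definition in SAP 2.2 and SAP 4: every Safety/ITT patient with a post-baseline assessment, documented clinical progression, or a known death from any cause within 91 days of first dose, whatever the reason for discontinuation.
2. State in SAP 3.2.7.1 that, for the binary PFS3 endpoint, any such death is a failure. This must override the rule that disregards deaths after EOT and the rule that censors at first dose; without it, change 1 is incomplete.
3. Report the treated patients left out of mITT, with their survival status at day 91.

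The cost is SAP wording and one small table or listing. Survival status and dates are already collected, so no new data are needed. The downside is that the PFS3 rate may be slightly lower.

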# 2.3 PER PROTOCOL (PP) POPULATION

The PP population will include all patients in the mITT population who have no important protocol deviations (IPD) which are determined to potentially impact efficacy analyses during the study. Protocol deviations will be identified prior to database lock and final analysis.

# **3 STATISTICAL AND ANALYTICAL PROCEDURES**

# 3.1 GENERAL STATISTICAL CONSIDERATIONS

### 3.1.1 Statistical Methods

Summary statistics will be presented as follows. For continuous variables, number of available observations (n), mean, standard deviation (s.d), median, first quartile (Q1), third quartile (Q3), minimum (min), and maximum (max) will be provided; 95% confidence interval for the median will be added as specified. For categorical variables, the number and percentage in each category will be displayed; missing categories will be added accordingly. Percentages will be based on the number of patients in the relevant analysis population.

Time-to-event data will be summarized using the Kaplan-Meier method.

By-patient data listings will be produced for data collected through the study (e.g., case report form, lab). All data listings that contain an evaluation date will contain a relative study day (Study Day). Pre-treatment and on-treatment study days are numbered relative to the day of the first dose of study drug, which is designated as Day 1. The preceding day is Day -1, the day before that is Day -2, etc.

All statistical analyses will be performed in SAS Version 9.4 or higher.

#### 3.1.2 Definition of Baseline

Assessment of change from baseline will include only those patients with both baseline and post-baseline measurements. The last evaluable/non-missing observation/assessment, including unscheduled visits taken before the first dose of study drug will be used as the baseline, unless otherwise specified.

#### 3.1.3 Visit Windows

All data will be tabulated per the evaluation visit as recorded on the electronic case report form, even if the assessment is outside of the visit window. With the exception of the baseline definition, unless otherwise stated in the analysis sections below, unscheduled visits will only be included in data listings.

